- To evaluate the effectiveness of 20 LPM HHNC therapy (Optiflow™ cannula and AIRVOT™2 device) – experimental therapy versus 5 LPM HHNC therapy (Optiflow™ cannula and AIRVOT™2 device) – control therapy on physiological outcomes in hospitalized subjects with cystic fibrosis during an acute exacerbation.

Secondary Objectives

- To determine if the experimental therapy has an effect on Quality of Life as measured by the Cystic Fibrosis Questionnaire - Revised (CFQ-R) compared to control therapy
- To determine the effect of the experimental therapy on sleep duration using actigraphy (Actiwatch® 2) and subjective sleep quality measured by the Leeds Sleep Evaluation Questionnaire (LSEQ) compared to control therapy
- To determine the effect of the experimental therapy on Quality of Life in respect to nasal dysfunction as measured by the Sino-Nasal Outcome Test (SNOT-20) compared to control therapy
- To determine the effect of the experimental therapy on comfort and ease of use using the non-validated comfort survey (VAS score) compared to control therapy

Primary Endpoints

- Change in sputum volume, cough transportability and hydration (% solids)
- Change in FEV₁ % predicted from admission to end of study.

STUDY DESIGN

The study is a single-center, randomized pilot study to evaluate the clinical effectiveness 20 LPM HHNC (Optiflow™ cannula and AIRVOT™2 device) experimental therapy, versus 5 LPM HHNC (Optiflow™ cannula and AIRVOT™2 device) control therapy, on specified outcomes in hospitalized subjects with cystic fibrosis during acute exacerbation.

Potential subjects will be identified in clinic before admission to the Children's Hospital of Richmond at VCU (CHoR) or Virginia Commonwealth University Medical. If potential subjects are not identified in clinic, they will be introduced to and informed of the study by a member of the study team within 24 hours of hospital admission.

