Assent from a subject will be obtained if they are aged 10 to 17 years along with informed consent from the eligible subject's parent or legal guardian. Informed consent will be obtained from subjects aged 18 years or older. All informed consent/assent discussions will take place in a private room and be documented according to the Pediatric Research Office's 'Informed Consent Process Cover Sheet'. Potential subjects and family members will be given as much time as necessary to determine if they would like to participate in the study. No study team member will be present during this period to minimize any possible coercion.

After informed consent is obtained the subject will be assigned a unique ‘Subject Identification Number.’ This number will consist of ‘VCUFP##’, where the first subject will be ‘VCUFP01’, the second ‘VCUFP02’, and so forth. This unique identifier will be used instead of the subject’s name, birth date, etc., to identify the subject for all study records and data.

After Subject Identification Number assignment is performed, randomization will occur. The study team will use the website www.randomization.com to randomize 30 study conditions (15 experimental and 15 control). The Study Coordinator will follow the randomization table chronologically as new subjects are consented.

This study is designed to accommodate 30 subjects (15 subjects per group) (Table 1). The study population will be determined from previously diagnosed CF patients who receive their CF care at CHoR and Virginia Commonwealth University. Subjects will be aged 10 years and older who are experiencing a CF exacerbation that requires hospital admission and therapy.

Table 1
STUDY DESIGN

Study Group	Assigned Intervention	Total Number of Subjects
Control Therapy	Low-Flow, 5 LPM (via Optiflow™ cannula) Heated (34°C), humidified air	15
Experimental Therapy	High-Flow, 20 LPM (via Optiflow™ cannula) Heated (34°C), humidified air	15

If a subject requests to withdraw from the study at any point, they are asked to inform the study doctor. Withdrawal from the study will not affect standard treatment the subject will receive for their CF exacerbation or ongoing treatment they may require. Upon withdrawal, the subject will forfeit any compensation for study participation.

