Study subjects may be involuntarily removed from the study if the study doctor believes that they are not complying with the study protocol and/or the study doctor believes it is in the best interest of the subject to stop participation.

Study devices/equipment

The experimental therapy will be administered using Optiflow™ nasal cannula with the AIRVO™2 humidifier. The AIRVO™2 device will heat and humidify ambient air and the Optiflow™ nasal cannula will deliver the heated (approximately 34°C) and humidified air via the nares at a flow of 20 LPM.

Fisher & Paykel Healthcare manufactures the Optiflow™ nasal cannula and the AIRVO™2 device. The Optiflow™ nasal cannula and AIRVO™2 device are being provided by Fisher & Paykel Healthcare for the study with no cost to the study subject. In addition, the subject will not be subjected to any further costs associated with the study. The study devices will only be available for use by the subjects that are enrolled in the study. The subject will be required to return the study device at the conclusion of the subject’s study involvement, or when the subject is discharged from the hospital (whichever occurs first).

The control therapy will be administered using Optiflow™ nasal cannula with the AIRVO™2 device. The nasal cannula will deliver heated (approximately 34°C) and humidified air into the subject’s nares at a flow of 5 LPM. This aims to mask the experimental and control therapy from the subjects and investigators.

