Subjects will be educated by the study coordinator on how the device works and how to set up the nasal cannula appropriately. Subjects will be instructed to sleep with the designated nasal cannula and device as instructed during their hospitalization, for a maximum of five nights. The time the device is placed in the subject's nares and the time when the device is turned on will be recorded regardless of the intervention group to which the subject is assigned. The nursing staff will be instructed to check that the individual is wearing the device (either experimental or control) appropriately throughout the entire night. Should the nursing staff notice the nasal cannula being worn incorrectly the nurse will attempt to correctly reposition without disturbing the subject or if this is not successful the subject will be awakened to ensure correct cannula placement. Following the overnight intervention, the nasal cannula will be removed from the device and washed with warm water and mild dish washing detergent. After rinsing with clean water the nasal cannula will be stored in a clean zip locked bag taped to the device during periods of non-use.

At study conclusion for each subject (Table 2. Study Procedures), the device will be cleaned and sanitized per manufacturer's guidelines. While not in use, the devices will remain clean/sanitized and stored appropriately within in the hospital facility.

Eligibility Criteria

Individuals must meet all of the inclusion criteria listed below in order to be considered as a potential study subject.

Inclusion Criteria:

- Confirmed diagnosis of CF
- Hospital admission for acute pulmonary exacerbation of CF
- 10 years of age or older
- Is able to comply with the procedures scheduled within the protocol
- Provide informed consent/assent

If an individual is eligible as defined by the inclusion criteria but is found to meet any of the exclusion criteria listed below, they will not be permitted to enroll in the study.

Exclusion Criteria:

- Receipt of any aerosolized experimental or investigational drugs within 1 month of enrollment
- History of ENT surgery, nasal bleeding or nasal polyps within 6 months of starting study
- Requires supplemental oxygen
- History of obstructive sleep apnea
- History of pressure headaches requiring therapy within 1 month of enrollment
- Other medical or psychological conditions in which the study doctor(s) believe(s) would inhibit the individual from being an appropriate study subject.

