BASELINE Day 1 (Approximately 9:00 AM)	
The device will be turned off (unless the subject has awakened earlier, in which case the subject can turn off the device when they wake).Sputum sample will be collected (where possible) or collection of previously produced sputum to research laboratory by study coordinator by 10:00 AM.Study coordinator will ensure that the nasal cannula is removed from the device and washed with warm water and mild dish washing detergent and rinsed thoroughly with clean water. The study coordinator will then place the nasal cannula in a clean zip locked bag taped to the device until required.Completion of the Leeds Sleep Evaluation Questionnaire (LSEQ)Completion of the device comfort survey (VAS Score).The study coordinator will collect the device log, and review the previous night's medical records (including any test results or medication dispensed).
TREATMENT PHASE Day 2 – 5 (PM)	
There will be no collection of produced sputum during this time.There will be no surveys completed during this time.The study coordinator and/or the study doctor will continue to review the subject's treatment and medication records.

Table 2
STUDY PROCEDURES

Time point	Procedure/Assessment
	
 Subjects will be allowed to go to sleep at whatever time they choose but must turn on the device before sleep onset and leave it on throughout the sleep period. The nursing staff will be instructed to ensure the subject continues to wear the device during the night. If for some reason the device comes off, or is turned off, the nurse will record the event and will attempt to correctly reposition without disturbing the subject or if this is not successful the subject will be awakened to ensure correct cannula placement. If the subject is discharged between Day 2 – Day 5, then the date of discharge will follow the 'Discharge' study procedure in place of the 'Treatment Phase' study procedure

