Statistical analysis of data will be performed using the JMP Pro 10 statistics package (SAS Institute, Cary, NC). Normality of data distribution will be visually checked and normally distributed data will be compared using two-tailed t-test and ANOVA. A $p < 0.05$ will be considered statistically significant. All results will be presented as means + the standard error of the mean.

QUALITATIVE EVALUATION

One sleep and three separate quality of life evaluations will be administered at various time-points according to Table 2 - Study Procedures. The information provided by the questionnaires will be transposed into the REDCap database by the study coordinator. All paper documents will be de-identified, the only identifier is the Subject Identification Number, which is kept in a locked cabinet, in the study coordinator's locked office.

Leeds Sleep Evaluation Questionnaire (LSEQ)

The Leeds Sleep Evaluation Questionnaire (LSEQ) is a 10-item, subjective, self-report, 5-10 minute paper and pencil measure designed to assess changes in sleep quality over the course of a psychopharmacological treatment intervention. The scale evaluates four domains: ease of initiating sleep, quality of sleep, ease of waking and behavior following wakefulness using paper and pencil. Developers initially validated the LSEQ in individuals aged 18-49 years. In the evaluation "initiating sleep" and the "quality of sleep" factors were correlated with one another while "awakening from sleep" and "behavior following wakefulness" factors were also correlated. Of the validated scales available to use for this study the LSEQ appears to be the most appropriate given the study being conducted.

Cystic Fibrosis Questionnaire-Revised (CFQ-R)

The Cystic Fibrosis Questionnaire-Revised (CFQ-R) is health-related quality of life (HRQoL) measure for children, adolescents and adults with CF. Initially it was developed through interviews with CF patients and healthcare providers and various focus groups and has since undergone comprehensive reliability and validity testing. This revised questionnaire is one of the most widely used HRQoL tests for CF. The CFQ-R measures how well an individual functions in a variety of domains, including Physical Functioning, Vitality, Health Perceptions, Respiratory Symptoms, Treatment Burden, Role Functioning, Emotional Functioning, and Social Functioning. This questionnaire is written for the intended age group in regards to language and length of questionnaire.

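### Subjects can be removed from the study for non-compliance after randomisation, with no final assessment and no as-randomised analysis, so the primary comparison can be biased if removals differ by arm

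*Combined protocol and SAP*

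**What the plan says.** The removal rule is in Study Design, after Table 1: "Study subjects may be involuntarily removed from the study if the study doctor believes that they are not complying with the study protocol". A second ground follows, where "the study doctor believes it is in the best interest of the subject to stop participation". No threshold for non-compliance is given.

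On timing, the same section says "After Subject Identification Number assignment is performed, randomization will occur", and Table 2 places randomisation at the Day 0 screening visit. On wear, Table 2 says that subjects "must turn on the device before sleep onset and leave it on throughout the sleep period", for up to five nights. Nurses check wear and record when the device comes off.

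The primary endpoints are changes in sputum volume, cough transportability and percent solids, and in FEV1 percent predicted from admission to end of study. Table 2 brings the final assessment forward only for hospital discharge before Day 6. Removed subjects are not mentioned. Data Analysis says that "normally distributed data will be compared using two-tailed t-test and ANOVA", with significance at p < 0.05. It names no analysis set, no as-randomised rule and no missing-data method.

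**The concern.** For device wear, the rule acts only after the subject has an assigned arm. Whether a subject keeps the cannula on all night may depend on how the assigned flow feels. The arms receive 5 and 20 LPM, and one secondary objective is "To determine the effect of the experimental therapy on comfort and ease of use" against control, so the trial treats a difference in comfort as an open question.

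If removals differ between arms in number or kind, and removed subjects would have had different outcomes, the retained groups are no longer the groups that randomisation made comparable. The primary comparison would then mix the effect of flow with the effect of selection. An outcome that was never measured cannot be restored at the analysis stage, so the rule has to be set in advance.

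**Working it through.** **Inputs from the documents.** 15 subjects per arm (Study Design, Table 1), two-sided t-test, alpha 0.05 (Data Analysis). The plan's only sample-size figure is 30. The sum 15 + 15 = 30 agrees, but nothing behind it can be reproduced, because no effect size, SD, power or dropout rate is stated.

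**Assumed inputs.** Net removals of 1 to 4 of 15; a difference D between retained and removed subjects of 0.5, 1.0 or 1.5 SD; no true effect of flow; within-arm SD of 1. The range of D is a choice made for illustration.

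**Bias.** Bias = (share removed in one arm − share removed in the other) × D. Each subject is 1/15 = 6.7% of an arm.

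| Net removals | D = 0.5 | D = 1.0 | D = 1.5 |
|---|---|---|---|
| 1 of 15 | 0.03 | 0.07 | 0.10 |
| 2 of 15 | 0.07 | 0.13 | 0.20 |
| 3 of 15 | 0.10 | 0.20 | 0.30 |
| 4 of 15 | 0.13 | 0.27 | 0.40 |

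For example, 3/15 × 1.0 = 0.20 SD. Equal removals give (3/15 − 3/15) × D = 0.

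**Against sampling error.** The standard error of the difference is √(1/15 + 1/15) = 0.365 SD. A bias of 0.20 SD is 0.20/0.365 = 0.55 of it. With 12 v 15 subjects the standard error is √(1/12 + 1/15) = 0.387 SD, about 6% larger, and the effect detectable with 80% power rises from 1.06 to 1.13 SD.

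**Type I error, by simulation under no true effect.**
- Each subject has a 20% chance of being a non-complier (3 of 15 expected) with outcome 1 SD worse, and non-compliers are removed from one arm only. The bias is 0.20 SD and the error rate about 7%, against about 5% when everyone is analysed as randomised.
- In a second model, one third of subjects have a mean lower by D, and removals come from that third at 20% v 0%. The error rate is 5.6%, 6.6% and 8.0% for D = 0.5, 1.0 and 1.5. The bias is slightly smaller (0.17 SD at D = 1.0), because some poorer-outcome subjects remain in the depleted arm.
- With 20% v 20% removal in the second model, bias is within 0.004 SD of zero and the error rate is 4.8% to 5.0%.

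The as-randomised baseline depends on how non-compliers are generated. Fixing exactly 3 in each arm makes that test conservative (about 3.3%) and suggests a doubling to about 6.5%. That contrast is partly an artefact; letting the number vary gives the fairer comparison of about 5% with about 7%.

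**The case against.** The rule is permissive and the same in both arms. Nothing in the documents says that removals will happen, will differ by flow or will relate to outcome. Comparing comfort asks a question and does not concede an answer. Non-compliance with the protocol also covers sputum, questionnaires and actigraphy, which need not depend on flow. Several features work against differential removal:
- Both arms use the same device and cannula, with masking of subjects and investigators intended.
- Ability to comply is an inclusion criterion.
- Nurses reposition the cannula or wake the subject.
- Treatment lasts at most five nights.

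The study is also a pilot that calls itself likely underpowered, and the illustrated bias for 3 removals is smaller than the standard error.

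Most of this stands as a limit on the size of the problem. One-arm-only removal is an unfavourable scenario, not a forecast. It does not remove the problem: masking may hide the arm from the doctor who decides on removal, but it cannot make the two flows feel alike. The plan also still states an effectiveness objective and tests at p < 0.05.

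A reader might infer that a removed subject has no later FEV1. The documents do not settle this. Table 2 lists tests as standard of care, and Study Design says that withdrawal does not affect standard treatment, so spirometry may exist. The plan does not say whether it would be used.

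**Conclusion.** The concern holds as a risk. As written, the plan permits removal after randomisation for a reason that may depend on the arm, provides no final assessment for those removed, and does not commit to an as-randomised analysis. The primary comparison can therefore be biased.

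The size cannot be derived from the documents. On the assumptions above, a net loss of 3 of 15 from one arm gives a bias of 0.10 to 0.30 SD, roughly a quarter to four fifths of a standard error, and a modest rise in type I error. All of this disappears if removals are balanced in number and kind.

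A stronger reading is tempting: that removals will be driven by the assigned flow, so the trial ends up comparing tolerators of 20 LPM with nearly everyone on 5 LPM, in favour of 20 LPM. The documents do not support it. They give no removal rates by arm, no expected direction and no link between tolerance and outcome. The point is worth acting on because the remedy is cheap.

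**What to change.** **Study Design.** State that non-compliance with the device alone does not end data collection. The Day 6 or discharge assessments and the follow-up assessments are still done unless the subject withdraws consent or the study doctor ends participation on the existing best-interest ground. That ground, and the doctor's discretion over device use, stay as they are.

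**Data Analysis.** State that:
- all randomised subjects with outcome data are analysed in their assigned arm regardless of device wear;
- removals, and missing sputum or FEV1, are reported by arm with reasons;
- a sensitivity analysis covers subjects without a later measurement, for example by assuming a range of worse outcomes for them;
- any compliers-only analysis is supportive.

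The sensitivity analysis is needed in any case, because Table 2 collects sputum only where possible, so some retained subjects will lack a later sample.

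**Cost.** A few sentences in two sections, some dilution of the effect by poor wearers, and a few extra assessments.

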Title: Evaluating High Flow Humidification Therapy in Patients with Cystic Fibrosis

NCT #: NCT02129803

Document date: May 25, 2016

Document Type: Protocol and Statistical Analysis Plan

Evaluating High Flow Humidification Therapy in Patients with Cystic Fibrosis

Protocol Number: HM20002205
NCT02129803

Sponsor: Virginia Commonwealth University

Funding Support: Fisher & Paykel Healthcare

Investigators: [name], MEngr, MD,MBA, FRCPC (Principal Investigator)
H. [name] (Co-Principal Investigator)
[name], MPH (Sub-Investigator)
[name] (Sub-Investigator)
[name], MD (Sub-Investigator)

Sites: Children's Hospital of Richmond at VCU/VCU Medical Center
Main Hospital, 7th Floor – Pediatric Services
[name]
[name], United States

Children's Hospital of Richmond at VCU
Children's Pavilion
[name]
[name], United States

VCU Medical Center
Critical Care Hospital, 3rd Floor
[name]
[name], United States

VCU Health Systems
[name]
[name], United States

INTRODUCTION

Mucus secretion and clearance is the primary physical defence of the airway epithelium.¹ Although mucus plays a defensive role, secretion retention is a common but serious problem in patients with chronic lung disease such as cystic fibrosis (CF).³ Poor ion transport and rapid respiratory rate are thought to play a role in secretion hypohydration in the CF airway and this is thought to contribute to poor mucus clearance, increasing pulmonary symptoms (pulmonary exacerbation), poor sleep quality and a reduction in quality of life (QoL).⁴ We have recently shown that high-flow, heated and humidified air delivered by a nasal cannula (HHNC) improves mucociliary clearance and clinical outcomes in young children requiring chronic mechanical ventilation.⁵ To date, nocturnal HHNC (without supplemental oxygen) therapy has not been studied in individuals diagnosed with CF but previous laboratory research suggests that this could be safe and beneficial.⁶

HYPOTHESIS

It is hypothesized that HHNC delivered at 20 liters per minute (LPM) via Optiflow™ cannula and AIRVOT™2 device may favorably affect the physical properties of the sputum and improve the subject's ability to clear secretions, resulting in beneficial clinical effects and improved quality of life.

STUDY OBJECTIVES AND ENDPOINTS

Primary Objectives

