Study data will be collected and managed using REDCap (Research Electronic Data Capture). REDCap is a secure web application designed to support data capture for research studies, providing user-friendly web-based case report forms, real-time data entry validation (e.g. for data types and range checks), audit trails and a de-identified data export mechanism to common statistical packages (JMP, SAS). REDCap also includes a powerful tool for building and managing online surveys. The database is hosted by VCU under award number UL1RR031990 from the National Center for Research Resources and NIH Roadmap for Medical Research, National Institutes of Health.

Only the study coordinators and the research assistants will have access to this password protected database.

With the exception of the ‘Informed Consent/Assent’ pages in the REDCap database, all subsequent pages will only identify the subject by the Subject Identification Number.

All hard copies of the signed Informed Consent/Assent documents will be kept in locked cabinet which is located in the study coordinator’s locked office. A copy of the signed Informed Consent/Assent will be scanned into the subject’s electronic medical record. Any other paper records that may be generated during the course of the study will be de-identified and labeled with the individuals Subject Identification Number and kept separated from the consent forms and locked in a cabinet in the study coordinator’s locked office.

OnCore

OnCore is a clinical trial management systems (CTMS) which will be used for recording and tracking regulatory approvals, staff training and safety management (SAE tracking and IRB reporting). The CTMS system was developed by Forte Research and widely used across academic research universities nationwide. The program is a secure web-based system hosted by both the VCU and MCV health systems. Only fully-trained, credentialed employees of VCU have access to this database. The study coordinator will be the only individual (besides individuals that manage OnCore) with access to data entered for this study into the OnCore database.

SPUTUM SAMPLE COLLECTION AND PROCESSING

Sputum collection is needed for evaluation of biophysical properties.

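### The plan names only SAE tracking for safety and defines no hours-of-use measure, so non-serious events such as nosebleed or headache are not systematically collected by arm and exposure can only be approximated

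*Combined protocol and SAP*

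**What the plan says.** **Safety.** The Introduction states that the overnight therapy is unstudied in this disease and offers only that "previous laboratory research suggests that this could be safe and beneficial". The exclusion criteria include "History of ENT surgery, nasal bleeding or nasal polyps within 6 months of starting study" and "History of pressure headaches requiring therapy within 1 month of enrollment". After randomisation, the only event capture named is in the OnCore section, which lists "safety management (SAE tracking and IRB reporting" among that system's uses. The primary and secondary objectives contain no safety endpoint, and Data Analysis contains no safety summary.

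**Tolerability.** Two secondary objectives compare the arms on comfort and ease of use (VAS) and on nasal dysfunction (SNOT-20). Table 2 places the VAS on Day 1 and at Discharge, and the SNOT-20 at screening, Discharge and the follow-up appointment. The Day 2 to 5 row rules out surveys.

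**Delivery.** Study devices/equipment says: "The time the device is placed in the subject's nares and the time when the device is turned on will be recorded". It also has nursing staff check wear overnight in both arms. The Day 2 to 5 row of Table 2 adds: "If for some reason the device comes off, or is turned off, the nurse will record the event". On Day 1 and at Discharge, "The study coordinator will collect the device log, and review the previous night's medical records". What the log contains is not described.

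**The concern.** This is a pilot of 15 subjects per arm that the Power Calculation section itself expects to be underpowered. Among the most useful things it can give a later trial are how the higher flow was tolerated and how much of it subjects received. Flow is the only planned difference between the arms (Table 1), and subjects may turn the device off when they wake.

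If 20 LPM led to more nosebleeds, headaches or early removal, non-serious events of this kind would enter the data only by chance. Without a defined measure of use, a null result on sputum or FEV₁ would also be hard to separate from shorter wear in one arm. Events that nobody asked about cannot be recovered at analysis.

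**Working it through.** The plan states no figure on this point, so the check is mainly a comparison of sections. The arithmetic only gives scale.

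**1. Could a non-serious nosebleed or headache be captured?**
- OnCore: serious events only.
- Table 2, Day 1 and Discharge: the previous night's records are reviewed, including medication dispensed. This happens on two mornings, while treatment may last up to five nights.
- Table 2, Days 2 to 5: treatment and medication records are reviewed. An event that needed no treatment could leave no trace.
- VAS: described as pointing to a face that shows a pain level, on two mornings.
- SNOT-20: described as 20 scored questions, at three visits. As described, it gives a score and not a dated event.
- Withdrawal and removal (Study Design): no reason is required to be recorded.

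Result: capture is possible but not systematic, and no summary by arm is planned.

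**2. Could hours of use be derived?**
- Placement time and turn-on time are both start times.
- Turn-off on Day 1 is at about 9:00 AM, or earlier on waking. The Discharge row sets no clock time. Neither row asks for the actual time to be recorded.
- Nurses record that the device came off or was turned off. No time or duration is asked for.
- Actigraphy gives sleep and wake timing, not device use.
- Data Analysis defines no adherence variable.

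Result: an approximate reconstruction is possible, and a log of unknown content might improve it. No defined measure exists.

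**3. Scale of the exposure question.** Flows are from Table 1; hours are assumptions, because the documents give none.
- Litres = LPM × 60 × hours. At 8 h: 20 × 60 × 8 = 9,600 and 5 × 60 × 8 = 2,400.
- Ratio of volumes = (20 × h₂₀)/(5 × h₅) = 4 × h₂₀/h₅.

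| Hours at 20 LPM | Hours at 5 LPM | Ratio of volumes |
|---|---|---|
| 8 | 8 | 4.0 |
| 5 | 7.5 | 100/37.5 = 2.67 |
| 2 | 8 | 2,400/2,400 = 1.0 |

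**4. What collecting events would allow with n = 15 per arm.** True event rates are assumptions.
- Zero events in an arm: one-sided 95% upper bound = 1 − 0.05^(1/15) = 0.181. The two-sided exact limit is 1 − 0.025^(1/15) = 0.218.
- Chance of at least one event = 1 − (1 − p)^15: 54% at p = 0.05, 79% at p = 0.10, 96% at p = 0.20.
- Power of a two-sided 5% comparison of proportions (normal approximation): about 27% for 10% versus 30%, and about 68% for 10% versus 50%.

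The data would therefore support description by arm, not a reliable test between arms.

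**The case against.** A reader might infer four stronger things. The documents do not support any of them in full.

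- **Only serious events are collected.** The OnCore section says what one management system is used for. Study data go into REDCap, whose forms are not described. What stands is that no procedure for non-serious events is set out.
- **Only turn-on times are recorded.** This is wrong. Placement time, nurse-recorded off events and a device log are also specified. Because the log is not described, it cannot be said to lack off times.
- **The trial cannot show whether 20 LPM was tolerated or delivered.** This is too strong. The VAS and SNOT-20 are compared by arm, and wear could be estimated from turn-on time, nurse notes and actigraphy.
- **The trial would report no such event.** This is also too strong. Early removal overnight is something nurses record, and a treated headache could appear in the medication review.

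Two further cautions are fair. The eligibility section gives no reasons for its exclusions, so reading nasal bleeding and pressure headache as device risks is a reasonable inference, not the plan's statement. Also, cumulative litres is an outside yardstick: the plan defines the arms by flow rate, and the hours used above have no source in it.

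These points narrow the concern but do not remove it. The existing sources are incidental, none is tied to a planned summary by arm, and no adherence variable is defined.

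**Conclusion.** The concern holds in this limited form and should be acted on. The plan sets out no systematic collection or by-arm summary of non-serious events. It also specifies no routine turn-off time and defines no hours-of-use measure, so exposure by arm could only be approximated.

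The size is bounded but not known. Depending on hours worn, the contrast in volume lies between fourfold (equal wear) and none (wear at 20 LPM one quarter of that at 5 LPM), assuming the higher-flow arm wears the device for no longer than control. With systematic questioning, an arm with no events could be reported with an upper bound of 18%. Without it, absence of reports supports no bound.

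The conclusion assumes that no unpublished case report form or device-log template already holds these items. If one does, what remains is to state it in the plan and define the summary. The point does not invalidate the primary comparison.

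**What to change.** 1. At the coordinator reviews already scheduled (Day 1, Days 2 to 5, Discharge), add a short dated yes/no checklist: nasal bleeding, headache, new oxygen requirement, and device removed at the subject's request, with the reason.
2. In the device log, add turn-off time and the time and duration of each interruption that nurses already record.
3. In Data Analysis, define hours of use per night. Report these and the event counts by randomised arm for every subject who started the device, as description and not as a test between arms.
4. If the flow setting is verified, keep that record with the coordinator, who already follows the randomisation table. Writing it on a log that others see would put the allocation on a study record, against the stated aim of masking subjects and investigators.

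The cost is a one-page REDCap form, a few log fields, modest extra data entry, and non-serious events that must then be reported. No additional visit is needed.
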